9.2 Collecting, Recording and Reporting of Adverse Events

Examination and close follow-up of parameters capturing subjects' oral health will be collected on case report forms (CRFs). These will be completed at every study visit, and data will be compiled into a pre-specified format and reviewed monthly by the PI for safety oversight. Serious adverse events (as defined in Section 9.1) will be collected from the time of enrollment until the last clinic visit and will be recorded in the electronic health records (EHR) system. At each study visit, the clinician or investigator will inquire

about the occurrence of SAEs since the last assessment. The investigator will review all source documentation related to study procedures for evidence of SAEs. Events will be followed for outcome information until they return to baseline or stabilize, or until 30 days after study completion or subject discontinuation. Subjects who have an SAE that is ongoing 30 days after study completion or discontinuation will be referred to an appropriate practitioner for continued care. Upon learning that a subject has experienced an SAE, the investigator must report the event to CPHS within 24 hours after becoming aware of the event.

On a monthly basis, the following events will be reported to every PI:

- Number of subjects experience severe complications and number of subjects enrolled. Severe complications include severe pain, continuous bleeding and severe swelling that needs prescription to control.
- Duration of observation of subjects experiencing severe complications and duration of observation of subjects enrolled.
- Any tooth loss, abscess, or other adverse oral health development requiring therapy or other intervention and the etiology (as captured in the dental history)
- Every PI will review the monthly reports for any safety signals.

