3. STUDY POPULATION

3.1 List the number of subjects to be enrolled

We will recruit 74 patients in total, and with a dropout rate of 15%, we will have a sample size of 64. With 64 patients, 32 in each group, we can detect a large effect size with 1 degree of freedom, alpha of 0.05 at 80% power.

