4. TRIAL SCHEDULE

There will be three appointments including the baseline appointment and two follow-up appointments (6 weeks and 12 weeks) after therapy. The details of each visit will be mentioned in 6.3. Study Visits and Procedures.

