The twelve weeks follow up will be the subjects last visit for this clinical trial. The patient will have clinical measurements taken as previously mentioned as well as possible radiographic measurements. If the patient has been diagnosed with peri-implant mucositis, recommendations will be made for continued maintenance of the diseased implant(s) and follow every 3 months. If the patient has been diagnosed with peri-implantitis, recommendations will be made for the possible need for surgical treatment.

d. Post Study Follow up and Procedures

[figure not shown]
The subjects will continue having routine maintenance appointments and/or treatments to follow up the outcomes related to the surgery and periodontal health in the periodontics clinic of UTSD. If the patients have symptoms or complications, the necessary treatments, will be performed.

e. Discontinuation Visit and Procedures

Subjects are free to withdraw from participation in the study at any time upon request. A subject may be discontinued from participation in the study for any of the following reasons:

1. Withdrawal of consent
2. Subject noncompliance with the protocol, as determined by the investigator
3. Any event or condition that would make continued participation in the study not in the best interest of the subject, as determined by the investigator
4. Pregnancy
5. Development of any medical condition that might affect the treatment and clinical outcomes, as determined by the investigator.
6. Initiation of any treatment or exposure that might affect the outcomes of implant therapy, as determined by the investigator.
7. Investigator discretion

Any subject with a serious adverse event, such as life-threatening diseases, hospitalization, that is ongoing at the time of discontinuation will be followed until the event returns to baseline, resolves, or stabilizes. If the serious adverse event does not meet these outcomes within 30 days after discontinuation or after study completion, the subject will be referred to an appropriate practitioner for continued care. If the study is discontinued, subjects will be referred back to the qualified clinicians for necessary dental care.

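### A treated subject who leaves early has no planned ascertainment of new-onset SAEs for the rest of the 12 weeks

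*Combined protocol and SAP*

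**What the plan says.** Section 9.2 sets the collection period: SAEs "will be collected from the time of enrollment until the last clinic visit". The main means of finding them is inquiry at each study visit "about the occurrence of SAEs since the last assessment", supported by a review of source records tied to study procedures. Section 4 fixes the visits: "There will be three appointments including the baseline appointment and two follow-up appointments (6 weeks and 12 weeks) after therapy". Section 6.3c adds: "The twelve weeks follow up will be the subjects last visit for this clinical trial".

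Two clauses reach past the last visit. Section 9.2 states: "Events will be followed for outcome information until they return to baseline or stabilize, or until 30 days after study completion or subject discontinuation". Section 6.3e provides that an SAE "that is ongoing at the time of discontinuation will be followed until the event returns to baseline, resolves, or stabilizes", with referral if it has not settled within 30 days.

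Section 6.3e is headed "Discontinuation Visit and Procedures". Its visible text lists reasons for discontinuation and the handling of ongoing SAEs, but describes no visit, timing or safety contact. On numbers, section 3.1 says: "We will recruit 74 patients in total, and with a dropout rate of 15%, we will have a sample size of 64".

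**The concern.** Section 6.3 places debridement and aPDT (or sham) in one combined baseline and treatment appointment, and section 4 schedules no further treatment session. A subject who leaves afterwards has therefore had the full intervention. Yet the search for harms depends on the subject coming back. A completer is asked at week 6 and week 12 about everything since the previous visit; a leaver is asked nothing more.

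The 30-day clauses do not close this gap, because they concern the outcome of events already known. They do not provide for finding events that begin later.

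This matters because leaving need not be unrelated to health. Sections 3.5 and 6.3e allow the investigator to discontinue a subject for an event, a new medical condition or a new treatment. Such subjects need not have withdrawn consent, so contact with them could still be possible. If they go unobserved, the adverse-event tables in section 11.2b rest on less observation than a reader would assume. If leaving differs by arm, the arms are also observed for unequal time.

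**Working it through.** **1. The plan's own numbers.** Inputs are 74 recruited, 15% dropout and 64 remaining (sections 3.1 and 11.1).

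- Inflating by multiplication: 64 × 1.15 = 73.6, which rounds up to 74 and matches the plan.
- Inflating by division: 64 / 0.85 = 75.3, which rounds up to 76.
- Forward check: 74 × 0.85 = 62.9, against the stated 64.

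The differences are at most two patients and do not affect this point. They give two counts of leavers: 74 − 64 = **10**, or 0.15 × 74 = 11.1, about **11**. Both are carried forward.

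**2. Time covered per subject**, taking *last clinic visit* as the last visit attended.

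- Completer: 12 of 12 weeks.
- Attends week 6, then leaves: 6 of 12 weeks (50%).
- Treated at baseline, never seen again: 0 of 12 weeks.

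**3. Time covered across the trial.** Planned post-treatment time is 74 × 12 = 888 person-weeks. With k leavers last seen at week L, observed time is (74 − k) × 12 + k × L.

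| Leavers k | Last seen | Observed | Unobserved | Share of 888 |
|---|---|---|---|---|
| 10 | baseline | 64 × 12 + 10 × 0 = 768 | 120 | 13.5% |
| 10 | week 6 | 64 × 12 + 10 × 6 = 828 | 60 | 6.8% |
| 11 | baseline | 63 × 12 + 11 × 0 = 756 | 132 | 14.9% |
| 11 | week 6 | 63 × 12 + 11 × 6 = 822 | 66 | 7.4% |

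The range is 6.8% to 14.9%. The rows are the two extremes for each k, and a mix of early and late leavers falls between them. The calculation assumes that every leaver was treated and ignores the replacement of withdrawn subjects that section 3.6 permits.

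**4. The other reading.** Section 6.3c calls the week-12 appointment the subject's last, so *last clinic visit* in 9.2 may mean the scheduled week-12 visit. The window is then nominally 12 weeks for everyone. A leaver does not attend that visit, however, and no other contact is specified. The period is defined but nothing is planned to fill it.

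**5. Other provisions that might fill it.**

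- The 24-hour report to CPHS (9.2) starts when the investigator learns of an event; it supplies no means of learning.
- Routine care in the school's clinic (6.3d) is not linked to SAE collection.
- Section 9.3 says all subjects will be monitored regularly, but gives no interval and no method for those who have left.

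**The case against.** The strongest reply is that the plan can be read as already having a fixed window to week 12, and that an event which becomes known must be reported whether or not the subject is still attending. Both points are fair. A reader might infer that a subject who withdraws on day 3 and is hospitalised on day 7 will go uncollected and unreported. The documents do not support that. The reporting duty has no attendance limit in its wording, section 9.1 says all unanticipated problems are reported, and the subject may still be seen in the same clinic. Moreover, under 9.1 the hospitalisation counts as an SAE only if it is unexpected, at least possibly related to participation, and indicates greater risk than was known. What remains is narrower: no planned route by which the investigator would come to know.

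Second, section 2.4b expects mild and reversible effects, section 11.2b plans descriptive tables and listings with no between-arm safety test, and 9.2 has duration of observation reported monthly. So qualifying events may be few, and shortened observation would at least be tracked. This limits the consequence. It does not recover missed events, and the end of observation for a leaver is still undefined.

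Third, a subject discontinued because of an ongoing SAE is followed under 6.3e. That is correct; the gap concerns separate events that start later.

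Finally, a figure is not shown just before 6.3e, and the data collection form in Appendix 1 is not in the text available. Either might describe a discontinuation contact, so the remark that none is described applies to the visible text only.

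**Conclusion.** The point holds as a gap in ascertainment. On either reading of *last clinic visit*, the text specifies no way to find a new-onset SAE after a treated subject has left. On the last-attended reading, about 7% to 15% of planned post-treatment safety time could go unobserved, given 10 or 11 leavers, all treated, last seen at either baseline or week 6. Lost time is not a count of lost SAEs, and the documents give no event rate from which to estimate one.

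Two stronger readings should be resisted. One is that early leavers contribute almost no safety follow-up: that fits only those never seen after baseline, since a subject who attends week 6 contributes half the window. The other is that the safety results are biased toward no harm: the documents give no information on leaving by arm or on its causes, so one can say only that the tabulation may be incomplete and may be biased. No efficacy result, power or alpha figure depends on this point.

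**What to change.** - **Section 9.2:** replace the visit-based end of collection with a fixed period for every treated subject, discontinued or not, running from enrollment to 12 weeks after the treatment session. State that new-onset as well as ongoing SAEs are collected.
- **Section 6.3e:** for discontinued subjects whose consent allows it, specify one phone contact or one review of the school's EHR at the week-12 date. Either describe the discontinuation visit or retitle the section.

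Extending collection only by the plan's existing 30 days would help less. It adds 30/7 = 4.3 weeks, so a subject last seen at baseline would reach 4.3 of 12 weeks (36%). With 10 such leavers, coverage would rise from 86.5% to (768 + 42.9) / 888 = 91.3%.

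The cost is a few sentences in an amendment, about 10 or 11 contacts or chart checks, and consent wording that permits safety follow-up after discontinuation. Subjects who refuse that follow-up will remain unobserved; reporting their number by arm would show how much of the gap is left.

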9.3 Safety Monitoring Plan

The purposes of the clinical monitoring activities are to ensure that the rights of human subjects are protected, the study is implemented in accordance with the protocol, and the integrity of study data is maintained. All subjects will be monitored for postoperative healing and tissue response at a regular interval while the entire oral health will be maintained throughout the study period.

10. DATA ANALYSIS

10.1 Data Quality Assurance

Data and measurements will be checked by two separate investigators as well as analyzed statistically to ensure that the data obtained is accurate, complete, and reliable.

11. SAMPLE SIZE AND STATISTICAL METHODS

11.1 Determination of Sample Size

We will recruit 74 patients in total, and with a dropout rate of 15%, we will have a sample size of 64. With 64 patients, we can detect a large effect size with 1 degree of freedom at an alpha equal to 0.05 with 80% power between the two treatments.

11.2 Statistical and Analytical Plans

a. General Consideration

We will present means and standard deviations for completeness of the report. The statistical significance level to test the primary endpoint was set at $p<0.05$.

b. Safety Analyses

Safety will be evaluated by tabulations of adverse events and will be presented with descriptive statistics at baseline and follow-up visits each month.

Adverse events will be classified as severe complications and summarized for baseline and follow-up visits.

All information pertaining to adverse events noted during the study will be listed by subject, detailing verbatim given by the investigator, preferred term, date of onset, date of resolution, severity, and relationship to procedure. The onset of adverse events will also be shown relative (in number of days) to the day of performing the surgery.

c. Statistical Analysis Plan

We will analyze these data sets using generalized linear mixed effects models with the appropriate error structure (e.g., binomial, poisson) and specifying treatment (control mechanical debridement vs mechanical debridement + aPDT) as a fixed factor and repeated measures of individuals over 0, 6, and 12 weeks as a random factor. Demographic data collected from patients will be included in analysis and will be adjusted for any confounders. All quantitative analyses will be performed in R Statistical Software (R Core Team 2017).

For microbiologic analysis, microbial DNA will be purified using the QIAmp DNA Mini Kit (Qiagen, Hilden, Germany) or Qiagen DNA MiniAmp kit (Qiagen, Valencia, CA, USA), according to the manufacturer's protocol. 16S rRNA gene V4 amplification and sequencing will be completed. 16S rRNA gene data analysis will also be completed for the plaque samples.

For immunologic analysis, the PerioPaper strips will be analyzed using multiplexed fluorescent bead-based immunoassay. Assessments will be made in triplicate, and for the statistical analysis, median of the replicates will be used.

12. Ethical Consideration

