2. HYPOTHESIS AND OBJECTIVES

2.1 Hypothesis

Null hypothesis: Antibiotic photodynamic therapy (aPDT) has no statistically significant advantage over traditional non-surgical mechanical debridement in improving clinical outcomes (# bleeding sites (BOP), probing depth reduction (PPD), or reduction in levels of pathologic microbes) in the treatment of implants with peri-implant inflammatory disease.

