2.2 Primary Outcome Measures

This study aims to compare clinical outcomes (change in BOP and PPD) after mechanical debridement of implant surfaces at sites exhibiting plaque induced inflammation with or without adjunctive aPDT. Bleeding on probing and periodontal probing depths will be assessed clinically through a periodontal probing exam at baseline, week 6, and week 12 follow up. Probing depth reduction endpoint value of 1mm (Bassetti et al. 2014, Morrison et al. 1980). Bleeding on probing endpoint value of 50-60% reduction of sites with BOP (Bassetti et al. 2014). Demographic and implant related variables will be analysed using multivariate analysis for correlation with peri-implant mucositis and peri-implantitis.

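### One alpha of 0.05 is set for a single primary endpoint, but two unranked primaries are named with no success rule or primary visit, and the stated model does not test the change they describe

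*Combined protocol and SAP*

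**What the plan says.** - **Alpha.** Section 11.2a: "The statistical significance level to test the primary endpoint was set at" p<0.05. The endpoint is singular and is not named.
- **Primary outcomes.** Section 2.2 aims to "compare clinical outcomes (change in BOP and PPD" between the arms. It lists the two together and gives each its own endpoint value. Neither is placed ahead of the other.
- **Visits.** Section 2.2 says that BOP and PPD "will be assessed clinically through a periodontal probing exam at baseline, week 6, and week 12 follow up". Neither follow-up visit is called primary there or elsewhere.
- **Model.** Section 11.2c plans "generalized linear mixed effects models with the appropriate error structure (e.g., binomial, poisson"), with treatment as a fixed factor and "repeated measures of individuals over 0, 6, and 12 weeks as a random factor". It states no fixed time term, no treatment-by-time term and no decisive contrast.
- **Sample size.** Sections 3.1 and 11.1 give 64 evaluable patients (32 per group in 3.1), alpha 0.05, 1 degree of freedom and 80% power for a large effect.

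No section ranks the two outcomes, says whether one or both must be significant, or shares alpha between them.

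**The concern.** Suppose that aPDT improves bleeding clearly and probing depth not at all. The plan does not say whether the trial has then succeeded, so the answer could be chosen after the results by arm are known. If a win on either outcome counts, each tested at 0.05, the chance of a false claim is higher than the 5% that 11.2a states.

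The model adds a second difficulty. The outcome in 2.2 is a change. A treatment factor with no time interaction estimates the difference between arms averaged over all three visits, including baseline, before any treatment has been given. Randomisation makes the expected baseline difference zero, so including it pulls the estimate towards zero. The test reported as primary would then not address the change that 2.2 describes.

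**Working it through.** **Inputs from the documents.** Alpha 0.05 for one endpoint (11.2a); two primary outcomes (2.2); visits at 0, 6 and 12 weeks (2.2, 11.2c); 32 per group and 80% power (3.1, 11.1).

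**Assumptions, because the documents give no figure.** Two-sided tests; one test per outcome; jointly normal test statistics; correlations as shown. Power uses a two-sample t-test with standardised effect d, taking the conventional d = 0.8 for a large effect.

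**1. The plan's own power figure.** With 32 per arm at two-sided 0.05, power is 80% at d = 0.71 and 88% at d = 0.8. The documents give no number for large, so both values are carried below.

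**2. Familywise error if either outcome suffices.** This is 1 − P(|Z1| < 1.96 and |Z2| < 1.96). At zero correlation it is 1 − 0.95² = 0.0975.

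| Correlation of the two test statistics | Familywise error |
|---|---|
| 0 | 9.75% |
| 0.5 | 9.1% |
| 0.9 | 7.0% |

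It falls to 5% only at perfect correlation. Without joint normality the general bound is 0.05 + 0.05 = 10%.

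**3. If both are required.** A false claim needs a true null to be rejected at 0.05 as well as the other test to succeed, so the error is at most 5%.

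**4. What the treatment factor in 11.2c estimates.** Take complete data, an identity link, unit SD at each visit, equal correlation ρ between visits, and a benefit δ at both follow-ups.
- Estimate: (0 + δ + δ)/3 = 2δ/3, a dilution of one third. For δ = 0.8 it is 0.533.
- SD of a patient's three-visit mean: √((1 + 2ρ)/3).
- SD of the week-12 change from baseline: √(2(1 − ρ)).

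| ρ | Three-visit average: d, power | Week-12 change: d, power |
|---|---|---|
| 0.3 | 0.533/0.730 = 0.73, 82% | 0.8/1.183 = 0.68, 76% |
| 0.5 | 0.533/0.816 = 0.65, 73% | 0.8/1.000 = 0.80, 88% |
| 0.7 | 0.533/0.894 = 0.60, 65% | 0.8/0.775 = 1.03, 98% |

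For reference, comparing week-12 values alone gives 88% at any ρ. The dilution of the estimate does not depend on ρ, but the effect on power does: at ρ = 0.3 a plain change score has less power than the average. If the model also gives both arms a common baseline mean, which randomisation justifies, the residual SD is about √(1 − ρ²). Then d is 0.8/0.954 = 0.84, 0.8/0.866 = 0.92 and 0.8/0.714 = 1.12, with power about 91%, 95% and 99%, above the average at every ρ shown.

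**5. Cost of Holm.** The smaller p-value is tested at 0.025, so familywise error is at most 0.025 + 0.025 = 0.05. In the worst case, where only one outcome responds, it must in general pass 0.025. Power then falls from 88% to 81% (d = 0.8) or from 80% to 71% (d = 0.71).

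**The case against.** The strongest reply is that the inflation is conditional. The plan never says that either outcome alone is enough, and if both are needed the 5% holds. That stands, and the error figures above apply only to the first case. It does not remove the gap, because the plan does not say which case applies.

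A second reply is that BOP and PPD are measured on the same implant, so zero correlation is unlikely. That also stands. The 9.75% is a ceiling, and 7.0% to 9.1% is the fairer range, though its correlations are assumed.

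Several stronger readings are tempting but not supported:
- **Separate testing at weeks 6 and 12 raises the error further.** Section 11.2c describes one model across all visits, and 3.1 and 11.1 refer to 1 degree of freedom. That fits one test per outcome.
- **The microbial outcome is a third primary.** The null in 2.1 does list "probing depth reduction (PPD), or reduction in levels of pathologic microbes" beside bleeding, but 2.3 makes microbiology secondary, and a study-wide hypothesis may mention a secondary outcome.
- **Sections 2.1 and 5.1 set opposing success rules.** One joins outcomes with an or, the other with an and. Both read as lists, and neither is worded as a decision rule.
- **The trial is too small if both must succeed.** That depends on an effect size that the documents do not give.

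It may also be said that a mixed model already deals with repeated visits. It accounts for the correlation between them, but it does not choose a contrast and does nothing about having two outcomes.

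**Conclusion.** The point holds as a gap that should be closed before any comparison by arm. The textual part is firm: one alpha for one unnamed endpoint, two unranked primaries, no primary visit and no success rule.

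The size is conditional. With either outcome sufficient, familywise error is about 7.0% to 9.1% at assumed correlations of 0.9 to 0.5 and at most 9.75% under joint normality with one test each. With both required, there is no inflation. A reader should not conclude that the trial's error rate is known to be inflated.

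The model part follows from 11.2c as written. Its treatment effect includes baseline, and for an equal benefit at weeks 6 and 12 the estimate is about one third too small. The exact fraction rests on complete data and an identity link. Any power loss depends on the within-patient correlation, which the documents do not give.

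**What to change.** Before any comparison by arm:

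1. State in 2.2 and 11.2a that BOP and PPD are tested with Holm at a two-sided familywise 0.05. If the sponsor prefers, use a fixed sequence with the order set in advance.
2. In 11.2c, add time and treatment-by-time terms, and make the week-12 between-arm contrast in change from baseline the primary test for each outcome. Week 12 is the natural choice: it is the final visit (6.3c) and the only follow-up with plaque and PISF samples (6.3b). Fitting a common baseline mean for the two arms is advisable, for the reason shown in step 4.
3. Label week-6, microbial and PISF results as secondary.

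**Cost.** No new data are needed. The change requires a protocol amendment with IRB review (12.2). Holm brings the worst-case loss of power shown in step 5. A fixed sequence keeps the full 0.05 for the outcome tested first, but the second outcome cannot then carry the claim alone.

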2.3 Secondary Outcome Measures

In addition to the clinical outcomes, plaque samples and peri-implant sulcular fluid (PISF) will be taken to assess the microbiologic and immunologic profile before and after treatment with or without aPDT. Subgingival biofilm samples will be collected using sterile titanium implant scalers and will be assessed at baseline and week 12 follow up. PISF will be collected from the tested implant site after clinical examination. The levels of interleukin (IL)-1 α , IL-1 β , IL-6, IL-8, IL-10, IL-12, IL-7A, tumor necrosis factor (TNF)- α , C-reactive protein, osteoprotegerin, leptin, and adiponectin will be determined using multiplex proteomic immunoassays.

2.4 Potential Risks and Benefits:

a. End Point – Efficacy

All eligible patients needing non-surgical treatment of peri-implant disease will receive the appropriate treatment of mechanical debridement. The mechanical removal of plaque around the implants is the gold standard of care in the treatment of implant inflammation. The patients in the adjunctive aPDT group may have improved healing as observed through surrogate clinical measures of inflammation (BOP, PPD), greater microbiologic reduction, and levels of key biomarkers in PISF that resembles peri-implant tissue health (Recker 2015).

b. End Points – Safety

1) Study related risks:

Initial mild pain, swelling, and bleeding related to non-surgical implant surface mechanical debridement. Potential for antimicrobial methylene blue dye to reversibly stain gingiva around implant site. Collecting PISF will not result in any additional side effects. Patient will not be provided medications for study

related pain. If patient reports pain after treatment will recommend over the counter analgesics such as ibuprofen or acetaminophen.

2) Protection against risk:

All efforts will be made to minimize risks to all and every participant. Laser safety protocols will be followed including laser safety mechanisms, labels and signage, safety zone implementation, proper eye protection for patient and clinician.

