reviewed with all patients including techniques to clean around implants. Mechanical debridement of implant surfaces will be completed with titanium scalers and ultrasonics removing supragingival and subgingival plaque. Antimicrobial photodynamic therapy will be done at implant sites by applying a photosensitizing dye methylene blue (0.1 mg/ml) with a disposable syringe from the bottom of pocket in a coronal direction. The methylene blue dye will be diluted from 1.0% to 0.1% before use. The dye will be applied topically confined to the epithelialized space surrounding the implant fixture and will not be internalized. After 5 minutes in situ, the surrounding gingival tissues will be irradiated at six sites around the implant using a diode laser with a wavelength of 660nm, providing an energy density of 10 J/site, 100mW power, time equal to 100 seconds. After irradiation, the site will be thoroughly rinsed with saline. Only pockets \geq 4mm will be treated with the diode laser as this is the threshold pocket for diagnosing peri-implant inflammation per the 2017 World Work Workshop (Heitz-Mayfield & Salvi, 2018).

Clinical Measurements

Implant sites will be evaluated at baseline, six weeks, and twelve weeks after treatment (2 follow-up visits in total). Improvement in sites resulting from a reduction in inflammation will be analyzed based on pocket depth, clinical attachment loss, bleeding on probing, and the presence of plaque. For clinical measurements, six sites around the implant will be measured: mesial buccal, mid buccal, distal buccal, mesial lingual, mid lingual, and distal lingual. Bleeding on probing will be evaluated by gently sweeping the periodontal probe just within the gingival sulcus of the implant and the presence or absence of bleeding will be recorded. The presence or absence of plaque will then be evaluated at six sites around the implant surface. Plaque sampling will be performed prior to the remaining clinical measurements at the baseline/treatment appointment and 12 weeks after treatment utilizing a titanium curette within the gingival sulcus of the inflamed site. Periodontal pocket depth is measured from the free gingival margin to the base of the pocket, with a UNC periodontal probe with 1mm measurement units. Clinical attachment loss is measured by subtracting the pocket depth from distance of the free gingival margin to the implant platform.

Microbiologic collection and analysis

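### Section 11.2b calls for monthly, day-dated safety data, but the first scheduled contact is week 6 and no visit has a stated question about the mild harms the protocol expects

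*Combined protocol and SAP*

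**What the plan says.** On presentation, section 11.2b states: "Safety will be evaluated by tabulations of adverse events and will be presented with descriptive statistics at baseline and follow-up visits each month". The same section promises a by-subject listing of all adverse events with onset date, resolution date, severity and relationship, and adds: "The onset of adverse events will also be shown relative (in number of days) to the day of performing the surgery".

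On the schedule, section 4 states: "There will be three appointments including the baseline appointment and two follow-up appointments (6 weeks and 12 weeks) after therapy". Section 6.3 confirms that there are two follow-up visits. Section 9.3 promises monitoring of healing at regular intervals but does not say what the interval is. No telephone call, diary or earlier visit is described.

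On the harms expected, section 2.4b names "Initial mild pain, swelling, and bleeding related to non-surgical implant surface mechanical debridement" and "Potential for antimicrobial methylene blue dye to reversibly stain gingiva around implant site".

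On what is collected, section 9.2 has the clinician or investigator ask at each visit about SAEs since the last assessment. Section 9.1 defines an SAE for this study as an unanticipated problem that also meets a seriousness criterion. Section 9.2 then adds a separate reporting line: "On a monthly basis, the following events will be reported to every PI". That report covers severe complications ("Severe complications include severe pain, continuous bleeding and severe swelling that needs prescription to control"), plus tooth loss, abscess and other oral events that need therapy or intervention.

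**The concern.** There are two gaps, and they compound. The first is timing: the safety section is worded for monthly follow-up visits that the schedule does not contain, and the unvisited period is the one right after the single treatment session. The second is scope: even when the patient is seen at week 6, the stated enquiry is about serious, unanticipated events. The harms that the protocol itself predicts fall outside it.

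At stake is the descriptive answer to what dye plus laser adds to debridement in minor harm. Mild events that have settled by week 6 would be unrecorded or dated from memory. A short adverse-event table could then be taken as evidence of good tolerability when it reflects limited asking.

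**Working it through.** The plan gives no figure to reproduce here. The check is of the schedule against the promised outputs, with illustrations whose assumptions are stated.

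**1. Inputs.** Follow-up visits at day 42 and day 84 (sections 4 and 6.3). 74 recruited and 32 per group evaluable (section 3.1). Enrolment limit of 24 months (section 3.6). The documents give no rate or duration for the expected harms.

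**2. Visits by month.**

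| Window | 28-day months | 30.44-day months | Scheduled follow-up |
|---|---|---|---|
| Month 1 | days 0-28 | days 0-30.4 | none |
| Month 2 | days 28-56 | days 30.4-60.9 | day 42 |
| Month 3 | days 56-84 | days 60.9-91.3 | day 84 |

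Two of three windows contain a follow-up visit. The empty one is the first.

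**3. Time from onset to first scheduled enquiry.** Lag = 42 − onset day. Onset on day 0, 1, 3 or 7 gives a lag of 42, 41, 39 or 35 days. Section 11.2b nevertheless asks for onset to the day and a resolution date.

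**4. What is asked at that visit.** The 9.2 prompt is for SAEs, and 9.1 requires an SAE to be unanticipated. Pain, swelling, bleeding and staining are anticipated in 2.4b, and the first three are described as mild. They fail the definition, so the 11.2b listing has no specified source for them at week 6 or week 12. Section 11.2b also names only one class of adverse event, the severe complication, which leaves mild events without a category.

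**5. Effect on the tables.** Let p1 and p0 be the true early-harm rates and s the fraction captured, assumed equal in the two arms and with no false reports.
- Recorded difference = s·p1 − s·p0 = s(p1 − p0).
- Recorded ratio = s·p1 / (s·p0) = p1/p0.

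The absolute difference shrinks by the factor s and the ratio is unchanged in expectation. With an assumed true difference of 20 points and s = 0.3 to 0.7, the recorded difference is 0.3 × 20 = 6 to 0.7 × 20 = 14 points. Expected counts per arm of 32 (rates and capture assumed):

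| True rate | True count | Recorded at s = 0.3 to 0.7 |
|---|---|---|
| 10% | 3.2 | 1.0 to 2.2 |
| 30% | 9.6 | 2.9 to 6.7 |
| 50% | 16.0 | 4.8 to 11.2 |

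**6. Patients treated meanwhile.** This applies only to an event that belongs in the monthly report and that nobody volunteers. The delay is 42 days, plus up to about 30 to the next report: 42 to 72 days, or 1.38 to 2.37 months. Assuming even accrual:
- over 24 months, 74/24 = 3.08 per month, giving 4.3 to 7.3 further patients;
- over 12 months, 74/12 = 6.17 per month, giving 8.5 to 14.6.

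The 24 months is a cap and not an accrual forecast, so neither range is a prediction.

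**The case against.** The best defence is that severe events do not depend on the schedule. The monthly report is built for complications that need a prescription or other intervention, and such patients tend to present themselves. Section 2.4b foresees patients reporting pain after treatment. This stands. A reader might infer that the monthly review is blind to early problems for 42 to 72 days; the documents do not support that. They support only that no scheduled contact occurs before day 42.

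Nor does the monthly report need monthly visits, since it can be compiled from whatever has come in. The monthly wording in 11.2b could likewise mean frequency of presentation. That reading is possible, but scheduled data would still come only from days 42 and 84.

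A reader might also infer that the safety comparison is biased towards no effect. That is too strong. No difference in capture between arms is shown, equal under-capture leaves the risk ratio alone, safety is descriptive only, and 2.4b attributes pain, swelling and bleeding to the debridement that both arms receive. The one harm listed for the dye, staining, would be expected to start at the session, so mainly its resolution date is at risk.

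Finally, the data collection form (Appendix 1) is named but its content is not available, so it may hold prompts that the text does not mention. The word surgery in 11.2b is a slip: with a single treatment session, day zero is clear.

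**Conclusion.** The point holds in limited form. Sections 4, 6.3, 9.1, 9.2, 9.3 and 11.2b do not agree on when safety is assessed or on which events are sought. As written, the expected mild harms have no stated prompt at any visit, and the first scheduled contact is about 42 days after treatment. The 11.2b listings can still be produced, so it would be wrong to say that the plan cannot deliver them. Their content for mild early events will be incomplete and recall-based.

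The size is a 35- to 42-day recall interval for events in the first week, and an absolute between-arm difference reduced in proportion to capture. The amount of reduction rests on assumed capture. That the harms are short-lived is inferred from the protocol's own description of them as initial, mild and reversible. Efficacy conclusions do not depend on this point. It merits correction because the repair is cheap and the safety tables are otherwise easy to over-read.

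**What to change.** 1. Add one short structured phone call or message in about the first week, made by existing unblinded treatment staff, with fixed questions on pain, swelling, bleeding, staining and any prescription, each with dates. A diary card handed back at week 6 would improve dating but would not shorten the 42-day gap.
2. Have the same staff ask the same questions at weeks 6 and 12, in addition to the SAE enquiry.
3. Use identical, neutral wording in both arms, and record the answers where the blinded examiners cannot see them. A report of stained gums would point to the test arm.
4. In 11.2b, replace the monthly-visit wording with presentation at baseline, the early contact, week 6 and week 12, by arm. Count onset from the treatment session, and provide a category for non-severe events.
5. Reconcile sections 4, 6.3, 9.2, 9.3 and 11.2b on visit frequency and on which events are actively collected, and check that the data collection form matches.

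The cost is about 74 short contacts, one CRF page and a protocol amendment. The recorded rate of minor events will rise, and a question about staining may cue some patients to their arm. If a count of patients treated before a signal is wanted, give it as a range under stated accrual (about 4-7 over 24 months, 9-15 over 12 months), or leave it out.
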